At the same time this symptomatology is identified as under-estimated and under-treated. Hubbard et al (2014), in accordance with the guidelines, suggest the need to introduce assessment of fatigue as a screening element for normal clinical practice. Interventions aimed at increasing physical activity, psychosocial and pharmacological support can benefit patients even if a standard treatment model has not been described to date (Bower, 2014). One of the difficulties highlighted in the literature is the correct identification of this syndrome. Scott et al (2011) stress the need for systematic studies in cancer populations with different types of cancer and at different stages of the disease using patient-oriented fatigue assessment tools. The Brief Fatigue Inventory (BFI) is one of the scales used precisely in the evaluation of this syndrome and has proved to be a reliable and easy to use tool, also validated in Italian (Mendoza et al 1999, Catania et al. 2013). Several authors have also shown that reduced physical activity and a worse quality of life are associated with fatigue (Witt et al 2002; Stark et al 2012, Warner et al 2008), particularly in young patients (Poort et al 2017) .

In the area of bone tumors, the available data on fatigue syndrome are extremely poor and only two studies have emerged from the literature search. The study by Granada-Cameron et al (2011) describes the experience of 11 new sarcoma patients undergoing chemotherapy treatment. Fatigue had been described as the prevalent symptom and was related to a worse quality of life.

Serveas et al (2003) observing patients two years after the conclusion of treatment for bone cancer found that in 28% of cases fatigue is a severe problem for patients.

Objective

The aim of the present study is to evaluate and describe the evolution over time of the fatigue and the quality of life of patients with bone tumor during the chemotherapy treatment and in the first phase of follow-up and to identify possible prognostic factors. Such knowledge is a necessary precondition for identifying patients and the periods most at risk due to the onset of fatigue, so as to be able to hypothesize adequate containment strategies.

Setting: Rizzoli Orthopedic Institute. Department of Chemotherapy

Methods

Design: observational study

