Population: all patients belonging to the Chemotherapy ward will be recruited consecutively for a new antineoplastic treatment protocol. The process of informing and collecting the participants' consent will take place during the first admission in which intravenous administration of the chemotherapy will be started. Potential participants will be identified / selected for recruitment through inclusion and exclusion criteria described below. Enrolled patients who will not continue the chemotherapy protocol within our Institute but at another facility will exit the study.

Inclusion criteria:

all patients diagnosed with bone tumors who start a new chemotherapy treatment protocol, both on admission and on an outpatient basis at the Chemotherapy ward for its antineoplastic treatment over 12 years of age. The NCCN Guidelines Cancer-Related Fatigue identifies appropriate screening with rating scales with scores from 0 to 10 precisely for patients older than 12 years.

Exclusion criteria:

patients with little knowledge of the Italian language due to the impossibility of completing the assessment scales.

Primary outcome:

the patient's Fatigue will be measured during the treatment period with antineoplastic drugs and part of the followup period. To this end the BFI scale validated in Italian will be used (Mendoza et al 1999; Catania et al, 2013) which includes 9 items with a score for each of 0 to 10 and a consequent total score from 0 to 90. The measurement will take place in 4 times: the day of enrollment, 6 months, 12 months and 24 months after enrollment.

Secondary outcome:

the quality of life of patients measured by the EORTC QLQ C-30 scale (Aaronson et al, 1993) and the level of autonomy measured by the TESS scale (Davis et al, 1996) in 4 steps: the enrollment day , at 6 months, at 12 months and at 24 months from enrollment.

Variables taken into consideration: through the literature search and the comparison between professionals of different disciplines (nurses, physiotherapists, oncologists) involved, a panel of variables was established to collect:

- Age
- sex
- BMI
- Smoking
- diabetes

- cardiopathies (hypertension, previous heart attack, ...)
- Comorbidity (pulmonary, renal, anemia, arthritis, neuromuscular complications, sleep disorders, pain, emotional distress)
- Diagnosis,
- presence of metastases at the entrance

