number of therapy cycles	OBSERVATION sheet (CRF): to be found in health documentation and then in the calculation sheet)	Nurse
tumor location	Enrollment form: to be reported in the calculation sheet	Nurse
surgery (date and type)	OBSERVATION sheet (CRF): report in a calculation sheet	Nurse
Pain	Measured with NRS scale. Data present in the BFI Sheet: to be reported in the calculation sheet	Nurse
Autonomy level	TESS scale: self-filled by the patient (6-12-24 months from enrollment)	Physiotherapist

Statistical analysis: The characteristics of the sample will be described using the mean and standard or median deviation and interquartile range for quantitative variables and absolute and percentage frequencies for qualitative variables. Simple and multiple linear regression analyzes will be performed and to identify predictors of primary and secondary outcome.

Sample size: In a pilot study of 19 patients at the Chemotherapy SSD the average BFI score was 31.6 with DS 19.1 at a mean follow-up of 5.2 months and DS 3.7. On the basis of this data, the number of variables taken into consideration equal to 15 in a multiple linear regression, an effect size of 0.1, an alpha value of 0.05 and a power of 80% the

number of patients to be enrolled is equal to 183. The sample size was calculated with Stata 15.0.

Duration of the study: The project lasted 5 years as follows:

Month 1-3 Meeting and training of the team involved in the study

Months 3–36 Patient enrollment and data collection.

Months 36-48 Construction of the database and preliminary analysis

Months 48-60 Follow-up and Statistical analysis of data

The approval date of the Ethics Committee will be considered as the starting date of the trial.

Safety assessment: as this is an observational study, patients will be treated in accordance with the rules of good clinical practice and in accordance with the protocols regularly used in the operating unit involved.

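### The first aim, the course of fatigue and quality of life over four visits, has no planned analysis that estimates within-patient change

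*Protocol*

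**What the plan says.** The Objective opens with the aim to "evaluate and describe the evolution over time of the fatigue and the quality of life of patients with bone tumor" during chemotherapy and early follow-up, and adds the identification of prognostic factors. For the primary outcome, BFI, "The measurement will take place in 4 times: the day of enrollment, 6 months, 12 months and 24 months after enrollment". QLQ-C30 and TESS are given the same four times under Secondary outcome. No visit is named as primary.

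The Statistical analysis section has two sentences. The first is descriptive: "The characteristics of the sample will be described using the mean and standard or median deviation and interquartile range for quantitative variables", with frequencies for qualitative variables. The second is "Simple and multiple linear regression analyzes will be performed and to identify predictors of primary and secondary outcome".

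The Sample size section rests on a pilot of 19 patients (mean BFI 31.6, SD 19.1) and on "the number of variables taken into consideration equal to 15 in a multiple linear regression, an effect size of 0.1", with alpha 0.05 and power 80%, giving 183 patients.

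Two statements bear on who remains in follow-up. Under Population, "Enrolled patients who will not continue the chemotherapy protocol within our Institute but at another facility will exit the study". The variable list includes "presence of metastases at the entrance", so patients with metastatic disease are enrolled and followed for 24 months.

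**The concern.** The aim stated first is about change over time, and the protocol schedules four measurements to serve it. Neither analysis sentence reaches that aim. The summaries are assigned to sample characteristics and the regression is assigned to predictors. The regression also has no defined dependent variable: it could be the score at any one visit, a change, or a summary of several visits.

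Three things are at stake:

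- The first aim would have no prespecified estimate of change with its precision.
- If the course were read off visit-by-visit means, the patients contributing would differ between visits. Should loss be related to fatigue, part of any apparent change would reflect who stayed.
- The visit used for predictors could be chosen after the data are seen, and a single-visit choice would leave collected scores unused.

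**Working it through.** **Inputs.** From the protocol: N = 183, 15 variables, effect size 0.1, alpha 0.05, power 80%, pilot BFI SD 19.1. Not in the protocol, so assumed: within-patient correlation ρ = 0.3, 0.5 or 0.7; 20–30% lost by month 24; odds of loss 1.5–3 per SD of the 6-month BFI.

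**1. The plan's own figure.** Overall F test with 15 and N − 16 degrees of freedom and noncentrality N·f².

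- 0.1 read as R²: f² = 0.1/0.9 = 0.111. Power is 79.96% at N = 182 and 80.26% at 183, so 183 is reproduced.
- 0.1 read as f²: power at 183 is 74.7%, and 201 patients would be needed.

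Under the reading that reproduces it, 183 is the size for one regression with one score per patient. It contains no visit, change or correlation term.

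**2. Precision of mean BFI change, enrolment to month 24, 183 complete patients.**

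- Paired: 1.96 × 19.1 × √(2(1 − ρ)/183) = 3.27 / 2.77 / 2.14 for ρ = 0.3 / 0.5 / 0.7.
- From visit means and SDs only: 1.96 × 19.1 × √(2/183) = 3.91.

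**3. Selective loss.** Let m be the mean standardised 6-month BFI among patients still present at month 24. Numerical integration over a normal score with logistic loss gives m from −0.079 (20% lost, odds ratio 1.5) to −0.270 (30% lost, odds ratio 3). The available-case bias at month 24 is corr(6, 24) × m × 19.1. The bias of a complete-case change from enrolment is [corr(6, 24) − corr(0, 6)] × m × 19.1.

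| Correlation pattern | Available-case 24-month mean | Complete-case change |
|---|---|---|
| Exchangeable: all pairs ρ | 0.3 × −0.079 × 19.1 = −0.5 to 0.7 × −0.270 × 19.1 = −3.6 | 0 |
| Decaying: ρ per 6 months, so corr(6, 24) = ρ³ | 0.027 × −0.079 × 19.1 = −0.04 to 0.343 × −0.270 × 19.1 = −1.8 | (0.027 − 0.3) × −0.079 × 19.1 = +0.4 to (0.125 − 0.5) × −0.270 × 19.1 = +1.9 |

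A likelihood model that uses the earlier visits is about unbiased under both patterns, because loss here depends only on an observed score (missing at random).

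**4. Predictors: efficiency only.** Take a constant effect over follow-up, complete data and exchangeable correlation. Averaging the 6, 12 and 24 month scores has variance (1 + 2ρ)/3 = 0.533 / 0.667 / 0.800 of one visit's. Intervals are 27% / 18% / 11% narrower, equivalent to a single-visit study of 183/ratio = 343 / 275 / 229 patients. With another correlation pattern, or an effect that varies over time, these figures change.

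**5. What the enrolment score does to a predictor coefficient.** Take a predictor worth 0.5 SD (0.5 × 19.1 = 9.55 points) equally at all four visits, with exchangeable correlation. Adjusting for the enrolment score leaves 9.55 × (1 − ρ) = 6.7 / 4.8 / 2.9; without it the coefficient stays at 9.55. The two models answer different questions.

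**The case against.** The strongest reply is that the aim is partly descriptive, that BFI is a quantitative variable, and that the descriptive sentence in a short translated section may have been meant to cover scores at each visit. A separate statistical analysis plan could supply the visit, the covariance structure and the missing-data assumption.

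Part of this stands. Details of that kind may properly sit in an analysis plan, and if scores are tabulated by visit, a point estimate of change can be read off. But the descriptive sentence is tied to sample characteristics, and visit means with SDs give neither a paired interval nor protection against selective loss. The protocol also fixes a method and sizes the study on it. An analysis plan that followed that text would still leave the first aim unserved.

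Several stronger readings are tempting and are not supported:

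- **That linear regression is the wrong method for predictors.** A single-visit or change-score regression is valid; the loss is in efficiency.
- **That the protocol commits to one score per patient, or to pooling visits as if independent.** It says neither. One score per patient is inferred from the sample-size calculation, and only if 0.1 means R².
- **That effects differing by period must be tested.** The protocol says "Such knowledge is a necessary precondition for identifying patients and the periods most at risk due to the onset of fatigue". This describes a later use of the results, not an aim of testing factor-by-time effects.
- **That a large bias at month 24 is shown.** No loss rate or correlation is given, and with decaying correlation the available-case bias may be close to nil.

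**Conclusion.** The mismatch holds: the first-stated aim is evolution over time, four visits are scheduled, and no planned analysis estimates within-patient change in BFI or QLQ-C30. It should be fixed before analysis, but it does not undermine the data.

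The cost in precision is modest to material: ±3.9 points against ±2.1 to ±3.3 for mean BFI change, given 183 complete patients, SD 19.1 at both visits and ρ between 0.3 and 0.7. The possible bias rests wholly on assumed loss and correlation. The available-case mean is off by about −0.5 to −3.6 points if correlation is exchangeable and about 0 to −1.8 if it decays with spacing. A complete-case change score is safe in the first setting but off by about +0.4 to +1.9 in the second. Only the likelihood approach is about unbiased in both, and it too requires missing at random. For predictors the point is unused information and an undefined outcome, not an invalid method.

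**What to change.** **Course over time.** Add to the Statistical analysis section: the course of BFI (primary) and QLQ-C30 will be estimated with a linear mixed model for repeated measures on all available visits, with visit (0, 6, 12, 24 months) as a categorical factor and unstructured within-patient covariance. Means by visit and changes from enrolment will be reported with 95% confidence intervals, assuming missing at random. Deaths and transfers will be reported separately, and the course interpreted for patients alive.

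**Predictors.** Use a mixed model of the 6, 12 and 24 month scores with visit and predictors known at enrolment. Report it with and without the enrolment score: with it, the coefficient shows what a predictor adds beyond enrolment fatigue; without it, its overall association with later fatigue. The sponsor should choose in advance which is main. The cycle count collected at month 24 should not be used to predict earlier visits.

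**Sample size.** State that 183 was sized for a single-score regression with 15 predictors and say which metric the 0.1 is. Restricting the model to factors known at enrolment takes some of the 15 listed variables out, so the basis must be restated if the set changes.

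**TESS.** First reconcile the schedule: four times under Secondary outcome and in the timing table, but 6, 12 and 24 months in the collection-methods table. If there is no enrolment TESS, report visit means and changes between follow-up visits, without enrolment adjustment.

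**Cost.** Revised wording, slightly more analysis work and reliance on missing at random. No new data or patients are needed.

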- type of chemotherapeutic protocol / drug that will be administered from the time of enrollment (Methotrexate, Cisplatin, Adriamycin, Ifosfamide, Elastomer Ifosfamide, Gemcitabine, Taxotere, Vincristine-Adriamycin-ifosfamide, Vincristine - phosphamide-Dactomycin, Ifosfamide-etoposide, Temiri, Topotecan, Cyclophosphamide, Eribulin)
- previous chemotherapy treatments: chemotherapy protocol / drugs already performed (Methotrexate, Cisplatin, Adriamycin, Ifosfamide, Elastomer Ifosfamide, Gemcitabine, Taxotere, Vincristine-Adriamycin-ifosfamide, Vincristine - phosphamide-Dactomycin, Ifosfamide-etoposide, Temiri, Topotecan, Cyclophosphamide , Eribulina) and number of cycles already carried out.
- number of therapy cycles carried out from the moment of enrollment (to be collected at the 24th month)
- tumor location
- surgery (date and type)
- Perceived pain measured with the NRS scale in the 4 expected data collection times

Data collection: the data will be collected at the Chemotherapy ward at the time of admission of the patient in the ward or of his access to the outpatient service. Nurses and the research physiotherapist will be responsible for collecting data by administering the assessment scales and consulting the patient's clinical documentation. Data collection times and specific collection methods are shown in the following tables:

1° day			
DIAGNOSIS/new protocol			
Consent/CRF	6 months		
BFI	BFI	12 months	
QLQ	QLQ	BFI	24 months
TESS	TESS	QLQ	BFI
		TESS	QLQ
			TESS

Variables	Collection methods	Responsible for the collection
Age	Health documentation - to be included in the enrollment form, then a calculation sheet	Nurse
Sex	Health documentation - to be included in the enrollment form, then a calculation sheet	Nurse
BMI	To be calculated: report the patient's weight and height at the entrance	Nurse
Smoking	OBSERVATION sheet (CRF): report in a calculation sheet	Nurse
diabetes	OBSERVATION sheet (CRF): report in a calculation sheet	Nurse
cardiopathies	OBSERVATION sheet (CRF): report in a calculation sheet	Nurse
Diagnosis	Enrollment form: to be reported in the calculation sheet	Nurse
presence of	Sanitary documentation: to be included in the	Nurse

metastases at the entrance	OBSERVATION (CRF) form, then calculation sheet	
type of chemotherapeutic protocol	Enrollment form: to be reported in the calculation sheet	Nurse
previous chemotherapy treatments	Health documentation - to be included in the enrollment form, then a calculation sheet	Nurse

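### The 183 patients give 80% power only for a model with at most 15 degrees of freedom, but 15 matches the number of bullets in a panel that names more quantities than that

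*Protocol*

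**What the plan says.** The Sample size section of the protocol takes "the number of variables taken into consideration equal to 15 in a multiple linear regression, an effect size of 0.1", adds alpha 0.05 and 80% power, and concludes that the "number of patients to be enrolled is equal to 183". It names neither the effect-size metric nor the test being powered.

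The Statistical analysis section says that "Simple and multiple linear regression analyzes will be performed and to identify predictors of primary and secondary outcome".

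The candidate variables are in the Methods list that opens "Variables taken into consideration: through the literature search". It has 15 bullets: age, sex, BMI, smoking, diabetes, cardiopathies, comorbidity, diagnosis, metastases at entry, current regimen, previous chemotherapy, cycles since enrolment, tumour location, surgery and pain. Several hold more than one item:

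- The current-treatment bullet, "type of chemotherapeutic protocol / drug that will be administered from the time of enrollment", lists 14 named drugs or regimens.
- The prior-treatment bullet, "previous chemotherapy treatments: chemotherapy protocol / drugs already performed", repeats those options and then adds "and number of cycles already carried out".
- The surgery bullet asks for both a date and a type.
- The comorbidity bullet names eight conditions.

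**The concern.** Power for the overall test in a multiple regression depends on the number of model degrees of freedom, not on the number of lines in a data-collection list. The Sample size section reuses the heading of the variable panel, and that panel has exactly 15 bullets, so the bullet count appears to have been entered as the degrees of freedom. A bullet with two quantities needs at least two terms if both are used, and a factor with 14 unordered options cannot be one linear term unless it is grouped.

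This calculation is the protocol's only justification of the study size. If the regression uses the panel as listed, the overall test has less than the stated 80% power at R-squared 0.10. Because the effect size is unlabelled, a reader also cannot tell directly what 183 patients are meant to detect.

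**Working it through.** **Inputs.** From the Sample size section: alpha 0.05, power 80%, 15 variables, effect size 0.1, N = 183. From the variable panel: the bullets and their contents.

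**Formula.** For an overall F test with u model degrees of freedom, the residual degrees of freedom are v = N − u − 1, the noncentrality is λ = N × f², and f² = R²/(1 − R²). Power is the probability that a noncentral F(u, v, λ) exceeds the 95th percentile of the central F(u, v).

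**Reproducing 183.** With R² = 0.10, f² = 0.10/0.90 = 0.111. At N = 183 and u = 15, v = 167 and λ = 183 × 0.111 = 20.3.

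- N = 182: power 79.96%.
- N = 183: power 80.26%.

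So 183 is exactly the minimum. The other readings of the effect size do not return it:

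- f² = 0.10 (R² = 0.0909) needs 201 patients; power at 183 is 74.7%.
- f = 0.1 (f² = 0.01) needs 1894.
- A test of one coefficient needs 74 (partial f² = 0.111) or 81 (partial f² = 0.10).

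The calculation is therefore an overall F test of R² = 0.10 with 15 degrees of freedom.

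**Counting terms from the panel.**

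- 17 = 15 bullets + 1 (prior cycles separate from prior regimen) + 1 (surgery date separate from surgery type), with every list still collapsed to one term.
- 27 = 14 other bullets + 13 indicators for the current regimen, if its 14 options are mutually exclusive.
- 28 = 14 other bullets + 14 yes/no indicators, if the options can co-occur.

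The last two are illustrative: they expand one bullet only and leave the rest at one term each.

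**Results, with R² held at 0.10 for the power and N columns.**

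| Model df | Power at N = 183 | N for 80% power | R² detectable at 183 with 80% power |
|---|---|---|---|
| 14 | 81.7% | 178 | 0.097 |
| 15 | 80.3% | 183 | 0.0995 |
| 16 | 78.8% | 187 | not computed |
| 17 | 77.4% | 192 | 0.105 |
| 27 | 64.6% | 233 | 0.127 |
| 28 | 63.4% | 237 | 0.129 |

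Fifteen is the largest number of degrees of freedom that keeps 80% at 183. Power falls further if prior regimens and comorbidities are also expanded.

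**Single predictors.** At N = 183, the partial R² detectable with 80% power for one 1-df predictor is 0.042 whether the model has 15, 17 or 27 terms, collinearity aside.

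**The case against.** The strongest reply is that nothing is miscalculated and that coding belongs in the statistical analysis plan, which is not at hand. The panel lists what will be collected; the protocol does not say that every item enters one model. Regimens can be grouped, comorbidity can be a yes/no or a count, the surgery date may serve only for timing, and prior treatment with its cycles can be one count with zero meaning none. Items can also drop out: cycles since enrolment are collected only at month 24, and pain appears both under comorbidity and as its own bullet. With 14 terms, power is 81.7%. The sample-size sentence could itself be read as fixing the model at 15 terms.

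Much of this stands as a limit on the size of the problem. A 15-term model is possible, the loss at 17 terms is small, and holding R² fixed while adding a dozen terms is the unfavourable assumption. The aim of identifying individual predictors is hardly affected.

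It does not remove the point. The protocol itself fixes 15, 183 and 80%, and its own panel, as listed, does not match the 15. No sentence limits the model to 15 degrees of freedom, and the calculation has no slack beyond 15.

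That the 15 came from the bullets is an inference from matching wording and count. The data-collection table also has 15 rows, but it omits comorbidity and includes the autonomy scale, which is a secondary outcome. Its rows for regimen, prior treatment and surgery are compound too, so that source would not rescue the figure.

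**Conclusion.** The concern holds and should be fixed. The arithmetic behind 183 is right for its inputs; the fault is that 15 listed variables are treated as 15 model degrees of freedom. The stated 80% holds only at 15 degrees of freedom or fewer. If every listed quantity enters, power is 77.4% at 17, the smallest such count. It is 64.6% at 27 if only the current regimen is expanded.

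These losses assume R² stays at 0.10. With 183 patients, 80% power is kept if R² is 0.105 at 17 degrees of freedom or 0.127 at 27. The shortfall concerns the overall test, and its size depends on coding that the protocol does not give. That 0.1 means R² is inferred from the exact reproduction, since the protocol does not label it.

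**What to change.** Keep 183. In the Sample size section, replace the phrase giving the number of variables and the effect size with: *R-squared = 0.10 (f-squared = 0.111), overall F test, 15 model degrees of freedom*. Then do one of the following.

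- **(a) Cap the model.** Add: *the multiple regression will use at most 15 model degrees of freedom*. The sponsor chooses the grouping.
- **(b) Restate the target.** For the degrees of freedom actually planned, give either the power at 183 (77.4% for 17, 64.6% for 27) or the R² detectable with 80% power (0.105 for 17, 0.127 for 27).

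The cost is wording and one recalculation, with no extra patients. Option (a) gives up detail on regimens and comorbidities. Option (b) means stating a lower power or a larger detectable R².

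### The sample size of 183 is the minimum number to analyse, but the protocol gives it as the number to enrol and states no allowance for loss

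*Protocol*

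**What the plan says.** The Sample size paragraph takes 15 variables in a multiple linear regression, "an effect size of 0.1, an alpha value of 0.05 and a power of 80"%, and concludes that the "number of patients to be enrolled is equal to 183". It gives no loss rate, no allowance and no replacement rule, and neither does any other section.

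Three other places bear on how many enrolled patients will have an outcome to analyse:

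- **Population:** "Enrolled patients who will not continue the chemotherapy protocol within our Institute but at another facility will exit the study". Consent is taken at the first admission, so this exit comes after enrolment.
- **Primary outcome:** for the Brief Fatigue Inventory (BFI), "The measurement will take place in 4 times: the day of enrollment, 6 months, 12 months and 24 months after enrollment".
- **Data collection:** "the data will be collected at the Chemotherapy ward at the time of admission of the patient"; the sentence goes on to include attendance at the outpatient service.

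The Statistical analysis paragraph says: "Simple and multiple linear regression analyzes will be performed and to identify predictors of primary and secondary outcome". It does not say which visit supplies the outcome.

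**The concern.** A power calculation for a regression returns the number of patients who must contribute an outcome and a full set of predictors. The protocol uses that number as its recruitment target, yet its own exit rule and a 24-month follow-up make some loss foreseeable. The number analysed at a follow-up visit will then be below 183, and the power below 80%, by an amount the protocol does not report.

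What is at stake is how the result is read. A null overall result would be set against a stated 80% power that the study did not have.

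**Working it through.** **Inputs.** From the Sample size paragraph: 15 variables, effect size 0.1, alpha 0.05, power 80%, stated number 183. The loss rate is not given in the protocol, so 5, 10, 20 and 30% are assumed for illustration.

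**Formula.** For the overall F test that R-squared is zero, with n analysed patients:

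- degrees of freedom: 15 and n − 16
- noncentrality: λ = n × R² / (1 − R²)
- power = P(F′ > F₀.₉₅), where F′ is noncentral F with those degrees of freedom and λ, and F₀.₉₅ is the central critical value.

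**Step 1: reproduce 183.** The protocol does not name the effect-size metric. With R² = 0.10:

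- n = 183: λ = 183 × 0.10 / 0.90 = 20.33, df 15 and 167, power 0.8026
- n = 182: λ = 182 × 0.10 / 0.90 = 20.22, df 15 and 166, power 0.7996

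So 183 is exactly the unadjusted minimum. Other readings do not return it: f² = 0.1 gives 201, and a test of one coefficient among 15 gives 74 (R²) or 81 (f²). No allowance can be hidden in 183. If f² = 0.1 was meant, 183 gives 74.7% before any loss.

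**Step 2: apply loss to 183 enrolled.** The number analysed is 183 × (1 − L), rounded down. For example, 183 × 0.90 = 164.7, giving 164.

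| Assumed loss L | Analysed n | Power at R² = 0.10 | R² detectable with 80% power | Partial R² detectable, one predictor |
|---|---|---|---|---|
| 0% | 183 | 80.3% | 0.100 | 0.042 |
| 5% | 173 | 77.1% | 0.105 | 0.044 |
| 10% | 164 | 74.0% | 0.111 | 0.046 |
| 20% | 146 | 66.9% | 0.124 | 0.052 |
| 30% | 128 | 58.7% | 0.141 | 0.059 |

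The last column uses 1 and n − 16 degrees of freedom.

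**Step 3: how much loss matters.** One lost patient still rounds to 80%. Seventeen (17/183 = 9.3%) leave 166 and 74.7%. Thirty (30/183 = 16.4%) leave 153 and 69.8%.

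**Step 4: which visit is meant.** The protocol does not fix it, but three things point to follow-up:

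- The Objective is to describe how fatigue evolves during chemotherapy and early follow-up and to find prognostic factors.
- One listed variable, the number of cycles since enrolment, is collected at month 24 and cannot predict an enrolment-day score.
- In the pilot, "the average BFI score was 31.6 with DS 19.1 at a mean follow-up of 5.2 months".

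**The case against.** The arithmetic and the missing allowance are not in dispute. The case on the other side is about reach.

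- **The loss is assumed.** The protocol reports no rate of transfer, death or withdrawal, and the large shortfalls come from the upper half of the range. At 5% loss, power is 77% and the detectable R-squared moves only from 0.100 to 0.105. This stands: the size is unknown and the table is illustrative.
- **The visit is not fixed.** An enrolment-day regression would be largely unaffected, and an unseen analysis plan may settle the visit. The pilot is weak evidence, because its mean and SD do not enter the calculation and its follow-up (SD 3.7 months) matches no single planned visit. This stands in part. The Objective and the month-24 predictor are better evidence, and both favour follow-up.
- **Only the overall test is affected.** The stated aim is to find predictors, and one strong predictor is little affected. True, but the overall 15-variable test is the one for which the protocol claims 80%.
- **The shift is small beside an effect size the protocol does not justify.** If the true R-squared were 0.12, power at 164 would still be 84%. That is a different assumption from the one stated; under the protocol's own 0.1, the claim fails.
- **Outpatient attendance also counts for data collection.** It does, but it is still attendance at the same Institute, and patients treated elsewhere exit in any case.

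**Conclusion.** The concern holds. Under the only reading tried that reproduces it, 183 is the bare minimum number of analysed patients, and the protocol labels it as enrolment. For a follow-up outcome, the stated 80% is met only with essentially no loss, which the exit rule and the 24-month schedule make unlikely.

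The shortfall is about 3 percentage points at 5% loss, 6 at 10%, 13 at 20% and 22 at 30% (80.3% minus the power in the table). This rests on three assumptions: the effect size is R-squared, the regression uses a post-enrolment BFI, and the loss lies in the assumed range. Confidence is high for the mislabelling and the absent allowance. The actual loss of power cannot be determined from the protocol.

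**What to change.** Reword the Sample size paragraph along these lines:

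> 183 patients with evaluable data at [the analysed visit] give 80% power for the overall test (15 variables, R-squared 0.10, alpha 0.05). With an expected loss of L% by that visit, 183 enrolled leave N evaluable, with power P or detectable R-squared R.

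This names both the visit and the effect-size metric. Take L from the ward's transfer and mortality records, and fill in N, P and R from the table above (for example, L = 10%: N = 164, P = 74%, R = 0.111).

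The cost is one paragraph and a slightly less favourable stated power. Visits, data collection and the exit rule do not change.

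Raising enrolment is optional. If the sponsor prefers to keep 80%, the figure is 183 / (1 − L), rounded up: 193, 204, 229 or 262 for 5, 10, 20 or 30% loss, which adds 10, 21, 46 or 79 patients.
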